## 3.3 NUMBER OF PARTICIPANTS

Fifty (50) patients will be studied.

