## 5 Image Analysis

### 5.1 Metastasis size evaluation:

- 5.1.1 A patient must have a single enhancing intraaxial brain metastasis of 5 mm or greater for study inclusion.
- 5.1.2 Metastases will be measured on axial T1 post-contrast imaging on a slice displaying the maximal tumor size using the longest diameter after appropriate magnification on the picture archiving and communicating system (PACS) monitors.
- 5.1.3 Only metastasis planned for radiation therapy will be assessed (for example, lesions present at baseline imaging that are planned for surgical resection will not be assessed).
- 5.1.4 For patients with more than one metastasis appropriate for study assessment, up to ten (10) lesions will be assessed.
  - 5.1.4.1 If there are more than ten lesions present, the five most caudal (lowest) and the five most cranial (highest) lesions that meet evaluation criteria will be tracked.

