# **7 STATISTICAL CONSIDERATIONS**

## **7.1 Definitions**

Brain metastases “**treatment response**” will be defined by size and contrast to noise ratio (CNR).

Size – treatment response in a lesion will be considered as a decrease in size of 30%. (see section 5.1)

CNR—treatment response will be considered as a decrease in T1 post-contrast CNR of at least 20% (see section 5.2) by standard T1 post contrast imaging for a lesion.

Metastases that do not meet these criteria for treatment response will be considered treatment failure.

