## 7.2 Sample Size

For each of the primary conspicuity endpoints, the objective is to estimate the ability of each imaging method (T2 weighted MRI, CEST MRI, Adv Diff, and DESE DSC) at identifying brain metastases at baseline. Standard of care qualitative T1 post-contrast imaging will be considered the gold standard. Each patient will have between 1 and 10 lesions, with an expected average of 4 lesions per patient. (For patients with more than 10 lesions, 10 will be chosen as described in Section 5.1.4.1.) The primary analysis will consider the largest lesion within each patient, and the analysis will be repeated considering all lesions. The sensitivity will be calculated along with the corresponding 95% confidence interval. With 50 patients, this confidence interval will be no wider than 14.5% on either side of the estimated proportion. The confidence interval around the proportion of total lesions detected will be tighter, depending on the total number of lesions.

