## 7.3 Analysis Plan

Patients are expected to have on average four brain lesions each. The primary analysis will be performed on the largest lesion within patients at baseline, and secondary analyses will consider all lesions. The sensitivity of each method at detecting lesions as determined by T1 weighting will be reported with 95% confidence intervals. Analyses will also be performed at the subsequent scans as numbers permit.

For the secondary endpoints that consider treatment response, for each of the imaging methods, at each time point, we will calculate the contrast to noise ratio (CNR) in patients with lesions that respond to treatment and in patients with local failure and will compare these by using a Wilcoxon rank-sum test. If numbers permit, analyses may be repeated using all lesions. Additionally, of the lesions that initially respond, some will subsequently grow in size after the initial response. Of these, some will be considered treatment change and some residual disease. The CNR will be compared between lesions with treatment change and those that are progressive disease using a Wilcoxon rank-sum test.

All statistical tests will be performed with two-sided tests with 5% Type I error rates. No adjustment will be made for the multiplicity of testing. We recognize that the Type I error rate overall will be greater than 5%.

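### The responder-versus-failure comparison in 7.3 is between patients with no rule for which lesion counts, and the all-lesion analysis that matches the per-lesion outcome is left optional

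*Combined protocol and SAP*

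**What the plan says.** **Outcome.** Section 7.1 defines response for the individual lesion, by size and by T1 post-contrast CNR. A metastasis that does not meet the criteria is a treatment failure.

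**Lesions available.** Section 3.3: "Fifty (50) patients will be studied". Section 7.2: "Each patient will have between 1 and 10 lesions, with an expected average of 4 lesions per patient". Section 5.1.4: "For patients with more than one metastasis appropriate for study assessment, up to ten (10) lesions will be assessed". The lesion-level measurements are therefore already part of the study.

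**Which lesions are analysed.** Section 7.3 opens with "The primary analysis will be performed on the largest lesion within patients at baseline, and secondary analyses will consider all lesions". For the primary sensitivity endpoint, section 7.2 firmly commits to repeating the analysis on all lesions.

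**The response comparison.** The next paragraph of 7.3 compares CNR, for each imaging method and time point, between patients whose lesions respond and patients with local failure, by a Wilcoxon rank-sum test. It then adds "If numbers permit, analyses may be repeated using all lesions". It names no representative lesion, no rule for a patient with both responding and failing lesions, and no number that would trigger the all-lesion analysis.

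**The later-growth comparison.** The same paragraph ends with a second rank-sum test, of treatment change against progressive disease. That test is between lesions and is not conditional on numbers.

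The documents give no expected failure rate, no within-patient correlation, no power for either comparison, and no method for correlated lesions.

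**The concern.** The outcome belongs to a lesion, but the test is between patients. To carry it out, someone must reduce each patient to one CNR value and one class, and the plan does not say how. With several lesions per patient, many patients may have both kinds, so the gap affects who is in which group.

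The analysis that avoids this problem is the one left optional, twice over: it depends on an undefined condition, and even then it is only permitted. The size of the failure group limits a comparison of this kind, so the plan may rely on its least informative version when a better one could be run on data already collected. Because nothing defines the trigger, whether the all-lesion result appears can also be settled after the data have been seen.

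**Working it through.** **1. The plan's own figure.** The only sizing figure is the 14.5-point maximum half-width in 7.2, for sensitivity with 50 patients. The exact (Clopper-Pearson) 95% interval at 25/50 runs from 35.5% to 64.5%, a half-width of 14.47 points, so the figure reproduces. It concerns the primary endpoint and says nothing about the response comparison.

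**2. Share of lesions and share of information.** 50 patients × 4 lesions = 200 lesions. One per patient leaves 1 − 50/200 = 75% unused. Lesions within a patient are correlated, so the information lost is smaller. With the design effect 1 + (4 − 1) × ICC, where ICC is the within-patient correlation (assumed):

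- ICC 0.3: 200/1.9 = 105 effective lesions; loss 1 − 50/105 = 52%.
- ICC 0.5: 200/2.5 = 80 effective lesions; loss 1 − 50/80 = 38%.

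**3. Mixed patients.** With four independent lesions and failure probability f, the chance that a patient has both kinds is 1 − (1 − f)^4 − f^4. For f = 10% this is 1 − 0.6561 − 0.0001 = 34%. For f = 25% it is 1 − 0.3164 − 0.0039 = 68%. Positive correlation lowers both figures.

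**4. Failure counts.** A one-lesion set is a subset of the all-lesion set. If instead a patient counts as failed when any lesion fails, each such patient contributes at least one failing lesion. Under either rule, the all-lesion set holds at least as many failures. This needs no assumed rate.

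**5. Power by formula.** For a rank-sum test, power ≈ Φ(d × √[(3/π) × n1 × n2 / (n1 + n2) / DE] − 1.96), with DE = 1 for one lesion per patient and 1 + 3 × ICC for all lesions. Assume d = 0.8 SD. Worked case at 10% failing:

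- One lesion (5 vs 45): n1n2/(n1 + n2) = 4.5; 0.8 × √(0.955 × 4.5) = 1.66; power 38%.
- All lesions (20 vs 180), ICC 0.3: 18/1.9 = 9.47; 0.8 × √(0.955 × 9.47) = 2.41; power 67%.

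| Lesions failing | Failures, one lesion vs all | Power, one lesion | Power, all lesions, ICC 0.3 | ICC 0.5 |
|---|---|---|---|---|
| 10% | 5 vs 20 | 38% | 67% | 55% |
| 20% | 10 vs 40 | 60% | 89% | 80% |
| 30% | 15 vs 60 | 72% | 96% | 89% |

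**6. Power by simulation, under each reading.** Assumptions: 50 patients, 1-10 lesions with mean about 4, 10-25% of lesions failing, a 0.74 SD shift (AUC Φ(0.74/√2) = 0.70), marker and outcome correlations each 0.2-0.5.

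| Analysis | Power |
|---|---|
| One lesion per patient, rank-sum | about 27-57% |
| Patient failed if any lesion fails, rank-sum | about 57-70% |
| All lesions, clustered by patient, jackknife errors, reduced degrees of freedom | about 65-98% (null error about 4-5%) |

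The lower ends of the last two rows are soft. A repeat run put them some 3 to 4 points lower, at 10% failing with outcome correlation 0.5. The ranges overlap because they span different settings; within each setting of the repeat run the all-lesion test had the highest power. Its advantage over the any-failing-lesion reading was smallest where failures were fewest and both correlations highest.

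**7. Why a plain all-lesion rank-sum will not do.** Ignoring clustering, its simulated null error was about 7% with both correlations at 0.3 and 11-12% at 0.5. A clustered test without a small-sample correction was also liberal, at up to about 10%.

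**The case against.** **The plan does not say one lesion per patient.** This stands. The largest-lesion rule is attached to the primary baseline analysis, and the same sentence gives secondary analyses all lesions, though it may refer to detection only. A reader might infer that 7.3 fixes the response test at one lesion and throws away three quarters of the data. The documents support only that the reduction to patient level is undefined. If the opening sentence does govern here, it conflicts with the optional wording a paragraph later, so the text needs settling either way.

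**The power contrast depends on the reading.** This also stands. If any failing lesion makes the patient a failure, the patient-level test does considerably better than under the one-lesion reading. A gain from all lesions remains.

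**A patient-level test with independent observations is a defensible anchor.** In part. An all-lesion analysis must handle clustering and needs enough patients with failures, so a condition on numbers is not absurd. It also answers a lesion-level question, gives more weight to patients with many lesions, and in the simulation assumes the same shift and noise for small and large lesions. These points argue for a corrected clustered test and a retained patient-level sensitivity analysis. They do not justify leaving the lesion-level analysis undefined.

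**The all-lesion result would be added and would not replace the first.** True, and 7.3 openly declines multiplicity control. That limits the harm from a late choice, but the choice stays open.

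**The necrosis questions are untouched.** Correct. A reader might extend the point to objectives 1.2.2.2-1.2.2.5, but the treatment-change versus progression test that serves them is already between lesions.

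**Conclusion.** The point holds for the responder-versus-local-failure comparison only. The unit of analysis does not match the outcome definition, the reduction to patient level is unspecified, and the lesion-level analysis is optional without a threshold. These follow from the text alone, as does the fact that using all lesions cannot reduce the number of failures.

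The size of the gain rests on assumed failure rates, effect size and correlations. In the settings examined, a properly clustered all-lesion test was the most powerful under either reading of the patient-level rule: by a wide margin over one lesion per patient, and by a smaller and more variable margin over the any-failing-lesion rule. It would be wrong to equate the 75% of lesions left out with 75% of the information; at correlations of 0.3-0.5 the design-effect figure is a loss of 52% to 38%.

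This should be changed, but it does not threaten the trial. The endpoint is secondary and unpowered, and the sample size rests on baseline sensitivity.

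**What to change.** In section 7.3, replace the conditional sentence with a firm, pre-specified comparison of CNR between responding and failing lesions, using all assessed lesions. Use a rank test clustered by patient, with a small-sample correction or patient-level resampling, and not a plain rank-sum. Make it the lead analysis for this secondary endpoint, because 7.1 defines the outcome per lesion. It also removes the need to class mixed patients.

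Keep the patient-level Wilcoxon test as the sensitivity analysis. State that it uses the largest lesion at baseline and that the patient is classed by that lesion's outcome.

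The cost is SAP wording and a somewhat more complex analysis, with patients who have many lesions carrying more weight. No extra scans or measurements are needed, since section 5.1.4 already has up to ten lesions per patient assessed.

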## 8 PROTOCOL MONITORING PLAN

This is not a treatment study, and no adverse effects are anticipated related to contrast-enhanced MR imaging. There is a tiny risk of an allergic reaction to the gadolinium-based and iodinated contrast agent for which the patient will go through regular Departmental screening.

